In order to prevent such diseases, addressing active periodontal diseases previous to implant surgery is mandatory; however, several factors associated with less prevalence of such diseases have been investigated pre-clinically and clinically. In this sense, a minimum of 1.5mm of bone surrounding the dental implant (Monje et al., 2019), a hygienic prosthesis (Serino et al., 2009, Katafuchi et al, 2018), a correct 3D prosthetically driven implant position (Herman et al., 2000, Buser et al., 2004) and enroll the patient in a tailored SPT program (Schwarz et al., 2018) are crucial in order to obtain long-term success and peri-implant health.

Several of these factors focus on improving oral hygiene access and motivate the patient to be more effective. Thus, a relevant surgical aspect that clinicians must consider at the time of implant placement, in order to allow a correct prosthetic design, is the distance between adjacent tooth-implant and inter-implant distances. For the horizontal space between adjacent tooth-implant, a distance of at least 1.5–2 mm from the adjacent teeth has been advocated especially for the anterior teeth (Van Oosterwyck et al., 1998). In addition, to prevent esthetic complications, it is advised to leave 3–4 mm of space between dental implants (Tarnow et al., 2000, Esposito et al., 1993). In this study, however, platform-matched implants were used.

In this sense, preclinical and clinical studies investigated the influence of inter-implant distance on marginal bone loss around platform-switched implants. In 2006, a preclinical study demonstrated that distances of 1, 2, and 3mm between implants did not result in statistically significant differences on marginal bone level around implants with a platform switch (Novaes et al., 2006). Likewise, Rodriguez-Ciurana et al. (2009) observed a minimal bone resorption (i.e., 0.62 mm) around platform-switched implants placed less than 3 mm apart.

Recently, a long-term retrospective study evaluated the biological complication rate of three types of implant-supported fixed dental prosthesis (non-splinted crowns, three splinted crowns and a 3-unit implant supported bridge) over two or three bone-level implants. The results of the investigation indicated that the prevalence of peri-implantitis was higher (16.7%) when three splinted crowns with three implants were used when compared with a 3-unit implant supported bridge over two implants (2.8%) (Ravidà et al., 2019).

Nonetheless, to our knowledge, no study has yet evaluated the association between the inter-implant distance of contiguous dental implants and peri-implant diseases.

Therefore, the aim of this study is to analyze contiguous dental implants and its peri-implant status depending on different inter-implant distances.

1.BACKGROUND

Implants have become a popular and widely used treatment option for treating partial and total edentulism. As the number of implants placed increases, so does the incidence of peri-implant mucositis and peri-implantitis. Several factors, such as a 3D correctly placed implant has been associated with better esthetic and overall outcomes on the long-term. Nevertheless, understanding a minimal threshold for inter-implant distance depending on type of implant might be critical to prevent such diseases.

2. OBJECTIVES

2.1 General objective

To evaluate the association between the inter-implant distance of contiguous dental implants and the prevalence of peri-implant diseases.

2.2 Specific objective

To evaluate the association between implant type (bone/tissue-level) and the prevalence of peri-implant diseases according to the inter-implant distance of contiguous dental implants.

3. HYPOTHESIS

3.1 General Hypothesis

A reduced inter-implant distance (i.e., < 3mm) of contiguous dental implants will result in a higher prevalence of peri-implant diseases.

3.2 Specific Hypothesis

Tissue level implants (i.e., one-piece implants) placed with an inter-implant distance < 3mm will result in a higher prevalence of peri-implant diseases than bone level implants.

4. MATERIAL AND METHODS

4.1 Study Design

The present research project has been designed as a multicentric cross-sectional study. The STROBE guidelines have been followed in the design of this observational study.

4.2 Ethical issues

The study will be performed after the approval of the Ethics Committee of the Universitat Internacional de Catalunya (UIC) and Faculdade de Medicina Dentária da Universidade de Lisboa (FMDUL) and will be intended to be registered in clinicaltrials.gov. Also, this research will be conducted according to the principles outlined in the Declaration of Helsinki (revised, amended, and clarified in 2013). In addition, all study participants will provide written informed consent before participating in the study.

4.3 Study population

Subjects will be selected from an electronic database collected at the CUO (UIC) / CU (FMDUL) and composed of patients treated with at least two contiguous dental implants before 2021. This investigation will use a stratified random sampling based on year of implant placement to select a representative sample of subjects with implant-supported restorations conducted during the period 2001–2020 at the CUO and CU. Then, two examiners ([name]) will contact patients by telephone

once every 2 days (with a maximum of 3 attempts) for an evaluation by the same investigators ([name]).

Criteria for subject selection will be as follows:

- The patient must be ≥ 18 years of age and systemically healthy;
- Partially edentulous patients, rehabilitated until 2020 (i.e., a minimum of 3 years of function time) with at least two contiguous implant-supported restorations in the maxilla or mandible;
- Screw or cemented-retained prosthesis;
- Fixed dental prosthesis (i.e., single crowns and partial prosthesis);
- No implant mobility.

Moreover, the exclusion criteria will be the following:

- Pregnant and lactating women;
- Patients who have taken systemic antibiotics during the 3 months prior to the examination;
- Patients being treated with drugs that may induce a gingival overgrowth;
- Patients undergoing orthodontic treatment (since it can influence periodontal diagnosis);
- Patients who have received mechanical debridement during the 3 months prior to the exam;
- Patients who have received surgical treatment for peri-implantitis;
- Psychophysical inability to carry out study procedures.

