4.4 Study Groups

Patients who meet the selection criteria will be included in the study and will be classified based on the inter-implant distance:

Group 1: Inter-implant distance ≤ 3 mm

Group 2: Inter-implant distance > 3 mm

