4.5 Sample Size Calculation

Sample size calculation has been based on the primary outcome variable (prevalence of peri-implant diseases). Previous studies have observed a patient-level prevalence of peri-implant diseases of 24%. Our hypothesis is that the prevalence of peri-implant diseases is higher when the inter-implant distance is reduced, around 44%. Accepting an alpha risk of 5% and a beta risk of 20% in a two-sided test, a total of 180 patients with adjacent dental implants (90 patients in each group) are required. Therefore, 90 patients will be recruited at each center. A loss rate of 12% has been

estimated.

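### Does excluding patients operated on for peri-implantitis undermine the comparison of disease prevalence between the two distance groups?

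*Combined protocol and SAP*

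**What the plan says.** Section 4.3 (Study population) aims, by random sampling stratified on year of implant placement over 2001–2020, to "select a representative sample of subjects with implant-supported restorations". Its exclusion list contains "Patients who have received surgical treatment for peri-implantitis", with no look-back period and no link to the contiguous implants under study. Two other items in the list do carry a window: systemic antibiotics, and "Patients who have received mechanical debridement during the 3 months prior to the exam". The inclusion criteria also require "No implant mobility".

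Section 4.4 (Study Groups) assigns distance after eligibility: "Patients who meet the selection criteria will be included in the study and will be classified based on the inter-implant distance".

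Section 4.5 names the outcome: "Sample size calculation has been based on the primary outcome variable (prevalence of peri-implant diseases)". It plans for 44% against 24% with 90 patients per group. Section 4.11 fits a logistic regression on study group and cofactors, which can only use included patients.

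The numbering of the available text runs from 4.7 to 4.11, so anything in 4.8–4.10, including an exclusion log, cannot be seen.

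**The concern.** The study asks how common peri-implant disease is at short and long inter-implant distances, yet it turns away people because they once had a severe form of that disease. Implants may date from 2001, so there could be up to about two decades in which surgery occurred. If the study's hypothesis is right and short distance promotes disease, past surgery may also be commoner in Group 1, and the exclusion might take more diseased patients from that group. The regression cannot repair this, because the missing patients are not in the data and have no recorded distance. A distance odds ratio that was too small or too large could then go unnoticed, and a claim to represent all patients with contiguous implants would be too wide. The contrast with the three-month windows on neighbouring items makes the open-ended wording look like an oversight.

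**Working it through.** **Inputs.** From section 4.5: p1 = 0.44 (reduced distance), p2 = 0.24 (reference), 90 per group, two-sided 5%. The documents give no figure for how many patients the criterion removes, so every removal share and every example table below is an assumption.

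**Step 1: the plan's own figure.** Planned odds ratio = (0.44/0.56)/(0.24/0.76) = 2.49. Power, with pooled variance under the null and unpooled under the alternative:

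Φ[(0.20·√90 − 1.96·√(2·0.34·0.66)) / √(0.44·0.56 + 0.24·0.76)] = Φ[(1.897 − 1.313)/0.655] = Φ(0.892) = 0.81.

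This agrees with the stated 80% at 90 per group, before any loss.

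**Step 2: what the exclusion does to the odds ratio.** Let f be the share of current cases removed in a group and g the share of current non-cases removed. Then

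observed OR = true OR × [(1−f1)/(1−g1)] / [(1−f2)/(1−g2)].

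Two consequences follow. If f = g within each group, the odds ratio does not move, however different the two groups' totals. If g = 0 (every operated patient is still a case), it moves only when f1 ≠ f2.

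**Step 3: do counts by group reveal the bias?** Take g = 0. Observed prevalence is p(1−f)/(1−pf), and the number excluded per 90 analysed is 90·pf/(1−pf).

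| Cases removed, Group 1 / Group 2 | Excluded per 90 analysed | Observed prevalence | OR | Power |
|---|---|---|---|---|
| 0% / 0% | 0 / 0 | 0.440 / 0.240 | 2.49 | 0.81 |
| 5% / 5% | 2.0 / 1.1 | 0.427 / 0.231 | 2.49 | 0.81 |
| 10% / 10% | 4.1 / 2.2 | 0.414 / 0.221 | 2.49 | 0.80 |
| 20% / 20% | 8.7 / 4.5 | 0.386 / 0.202 | 2.49 | 0.78 |
| 5% / 2.5% | 2.0 / 0.5 | 0.427 / 0.235 | 2.42 | 0.79 |
| 10% / 5% | 4.1 / 1.1 | 0.414 / 0.231 | 2.36 | 0.75 |
| 5% / 10% | 2.0 / 2.2 | 0.427 / 0.221 | 2.63 | 0.85 |
| 20% / 10% | 8.7 / 2.2 | 0.386 / 0.221 | 2.21 | 0.67 |

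The 10%/10% row has clearly unequal counts and no bias. The 5%/10% row has nearly equal counts and a shifted odds ratio. If distance really raises prevalence, unequal counts are what an unbiased exclusion produces. So a log by group cannot tell a reader whether bias is present.

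**Step 4: what worst-case bounds would add.** Take assumed analysed tables, add the excluded patients back under the four extreme codings, and use Wald 95% intervals on the log odds ratio.

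Near the planned effect, 40/90 against 22/90: OR 2.47 (1.31–4.67). Adding back 4 and 2 patients:

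- all cases, 44/94 v 24/92: 2.49 (1.35–4.62)
- all non-cases, 40/94 v 22/92: 2.36 (1.26–4.42)
- Group 1 cases, Group 2 non-cases, 44/94 v 22/92: 2.80 (1.50–5.24)
- the reverse, 40/94 v 24/92: 2.10 (1.13–3.90)

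Borderline, 36/90 against 22/90: OR 2.06 (1.09–3.91). Adding back 2 and 2:

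- all cases, 38/92 v 24/92: 1.99 (1.07–3.72)
- all non-cases, 36/92 v 22/92: 2.05 (1.08–3.87)
- Group 1 cases, Group 2 non-cases, 38/92 v 22/92: 2.24 (1.19–4.22)
- the reverse, 36/92 v 24/92: 1.82 (0.97–3.41)

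Only the last interval includes 1. It requires every operated Group 1 patient to be healthy now and every operated Group 2 patient to be diseased now.

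**The case for a change.** The best case for acting is that the step is cheap. Eligibility, examination and main analysis would stay as they are. The sponsor would log the distance group of patients who fail only on this criterion and add four two-by-two tables. Under the assumed shares from 5%/2.5% to 20%/20% that is about 3 to 13 charts per 180 analysed (2.0 + 0.5 up to 8.7 + 4.5). With a result close to the significance threshold, two patients per group can decide it, and section 4.1 says STROBE guided the design.

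Part of this stands. The text gives no reason for the criterion and names no restricted target population, and readers would be helped by the number excluded. The rest is weaker:

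- The bound is unadjusted, so it does not bound the adjusted model in section 4.11, and it removes no bias.
- It needs distance from the records of people who did not join, some with implants placed as early as 2001. Section 4.2 covers consent only for those who do: "all study participants will provide written informed consent before participating in the study".
- It singles out one selection route. Recent debridement, implant mobility and failure to respond after three calls may also relate to disease, and bounding one of them could reassure wrongly about selection as a whole.
- The differing time limits are not a contradiction. Past surgery may alter what an examination finds in a way that is not comparable with a recent course of antibiotics or a recent cleaning.
- The background speaks of rising implant numbers and says "so does the incidence of peri-implant mucositis and peri-implantitis", but only surgery for the second condition excludes. The smaller removal shares may therefore be the nearer ones.

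**Conclusion.** The observation is accurate: the criterion has no time or site limit, and eligibility depends partly on outcome history. It does not show that the plan gives a wrong answer. Among patients without prior surgery for peri-implantitis the comparison is well defined, and the price is a narrower population, which is a fair trade-off for examination findings not altered by surgery.

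Any bias in the distance odds ratio is unproven, with size and direction unknown. In the table it runs from none (equal shares) to 2.21 or 2.63 in place of 2.49, and that rests on assumed shares with every operated patient still a case. If 44% and 24% already describe eligible patients, the power losses shown are already in the plan. Exclusion counts by group would not resolve the question, and the bounds overturn a conclusion only for a result chosen to be marginal, under one extreme coding.

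What remains is for the write-up: name the population as patients without such surgery, confine the prevalence and association conclusions to it, and give the number excluded. Analysts can do this without amending the plan, and a bounding table, if produced, would be exploratory.

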4.4 Study Groups

Patients who meet the selection criteria will be included in the study and will be classified based on the inter-implant distance:

Group 1: Inter-implant distance ≤ 3 mm

Group 2: Inter-implant distance > 3 mm

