4.7 Data collection

Two calibrated investigators will consecutively call patients for an appointment and will be responsible of enrolling the patients.

The study variables will be recorded in a case report form (CRF) specially designed for the study. Each study patient will be assigned a numerical code comprising a 3-digit patient code (assigned correlatively as they are included in the study). Only the study investigators will be able to identify the patient by their code.

Medical history of the patients will be reviewed. Patients will also be advised of their role in this study and asked to sign an informed consent. After giving consent, patients will undergo a full-mouth manual probing using a periodontal probe PCP-UNC 15 (HuFriedy®, [name]) to determine their periodontal and peri-implant status and, if necessary, a full-mouth periapical radiographic examination will be performed.

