4.11 Statistical analysis

The Shapiro-Wilk test will be used to determine if the data follow a Gaussian distribution. Descriptive statistics will be expressed as mean \pm standard deviations (SD), median or percentage for parametric, non-parametric and categorical data, respectively.

Comparisons between study groups will be performed using Chi-square test (Fisher's exact test with observed frequencies <5) for categorical variables while continuous variables will be tested using Student's T test (Mann Whitney U test in variables that are not normally distributed). For ordinal variables, the linear relationship will be calculated using Kendall's tau coefficient.

A final logistic regression model will be performed including the prevalence of peri-implant diseases as a dependent variable. The study group and other potential cofactors will be included as independent variables.

Intra- and inter-examiner reproducibility will be calculated with the intraclass correlation coefficient.

A p-value <0.05 will be considered statistically significant. R Studio software will be used for all analyses.

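### For patients with several inter-implant gaps, the plan does not say which gap sets the group or tie disease to that gap, so implant count can bias the comparison

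*Combined protocol and SAP*

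**What the plan says.** - **Eligibility (section 4.3).** Patients must be rehabilitated "with at least two contiguous implant-supported restorations in the maxilla or mandible". There is no maximum, so three or more implants in a row, or more than one contiguous site, are allowed.
- **Grouping (section 4.4).** "Patients who meet the selection criteria will be included in the study and will be classified based on the inter-implant distance", with distance in the singular. The first group is "Group 1: Inter-implant distance ≤ 3 mm" and the second is everything wider.
- **Aim (introduction).** "the aim of this study is to analyze contiguous dental implants and its peri-implant status depending on different inter-implant distances". The specific hypothesis (section 3.2) is also about implants: "Tissue level implants (i.e., one-piece implants) placed with an inter-implant distance < 3mm will result in a higher prevalence of peri-implant diseases" than in bone-level implants.
- **Sample size (section 4.5).** "Previous studies have observed a patient-level prevalence of peri-implant diseases of 24" per cent, against about 44% when the distance is reduced; 90 patients per group.
- **Examination (section 4.7).** Probing covers the full mouth. For radiographs, "if necessary, a full-mouth periapical radiographic examination will be performed".
- **Analysis (section 4.11).** Chi-square or Fisher's test between groups, then a logistic model: "The study group and other potential cofactors will be included as independent variables". The section names no unit of analysis, no clustering term and no implant count.

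**The concern.** The scientific question is about a gap and the two implants that border it. The grouping is by patient. With one pair these coincide. With several gaps two things are left open: which gap decides the group, and whether disease at an implant away from that gap makes the patient a case.

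Both matter because implant count acts on both sides of the comparison. More implants mean more chances that at least one is diseased. More gaps also change the chance of being labelled narrow, by an amount that depends on the rule. Count is then a confounder created by the classification, and the main odds ratio depends on a choice the text does not state. If that choice is made after the data are seen, it can move the estimate in either direction. The implant-type objective has the same difficulty in any patient whose gaps straddle 3 mm.

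**Working it through.** **1. The plan's own figure.** Inputs from section 4.5: 24% vs 44%, two-sided 5%, power 80%.

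n per group = [1.96·√(2·0.34·0.66) + 0.842·√(0.24·0.76 + 0.44·0.56)]² / 0.20² = (1.313 + 0.551)² / 0.04 ≈ 87.

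With 90 per group, power is 81.4%. The planned odds ratio is (0.44/0.56)/(0.24/0.76) = 2.49. So 180 reproduces, before losses, as a count of patients with one exposure and one outcome each.

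**2. Who is affected.** Let each gap be ≤ 3 mm with probability q, independently (assumed). With m gaps, the narrow group holds 1 − (1 − q)^m of patients if any narrow gap counts, and q^m if all gaps must be narrow.
- m = 1: the two rules agree.
- m = 2, q = 0.5: 75% vs 25%, so 50% of these patients change group.
- m = 2, q = 0.3: 51% vs 9%, so 42% change group.

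With 2/3/4 implants in 50/30/20% of patients (assumed) and q = 0.5, the share with gaps on both sides of 3 mm is 0.30·0.50 + 0.20·0.75 = 30%. Over q = 0.3 to 0.5 and gap correlation 0 to 0.5, the simulated share is 17–30%. With 2/3 implants in 70/30%, it is 9–15%.

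**3. Bias with no distance effect, by hand.** Assume half the patients have 2 implants and half have 4, and each implant is diseased independently with probability 0.10 whatever the spacing. Any-implant disease is then 1 − 0.9² = 19.0% and 1 − 0.9⁴ = 34.4%. Take the any-gap rule with q = 0.5 for everyone. The narrow shares are 0.5 and 1 − 0.5³ = 0.875.
- Narrow group: (0.5·0.190 + 0.875·0.344)/1.375 = 28.8%.
- Wide group: (0.5·0.190 + 0.125·0.344)/0.625 = 22.1%.
- Difference: +6.7 points, with no true effect.

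The same arithmetic for other rules, and with q allowed to differ by implant count, gives (narrow minus wide, percentage points):

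| q for 2 / 4 implants | any gap narrow | all gaps narrow | one random gap, any-implant disease |
|---|---|---|---|
| 0.5 / 0.5 | +6.7 | −6.7 | 0 |
| 0.3 / 0.8 | +11.6 | +3.4 | +7.8 |
| 0.6 / 0.2 | −1.7 | −10.8 | −6.4 |

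**4. Null odds ratios by simulation.** 2/3/4 implants in 50/30/20%; all inputs assumed.

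| Chance of a narrow gap, 2/3/4 implants | any gap | all gaps | random gap, any-implant disease |
|---|---|---|---|
| 0.4 / 0.4 / 0.4 | 1.22 | 0.81 | 1.01 |
| 0.3 / 0.6 / 0.8 | 1.45 | 1.11 | 1.28 |
| 0.6 / 0.3 / 0.2 | 0.93 | 0.69 | 0.81 |

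With spacing unrelated to count and the other assumptions varied (q 0.3–0.5, gap correlation 0–0.5, any-implant prevalence 24–30%), the ranges are 1.10–1.26, 0.76–0.91 and 0.98–1.02. In points, any-gap gives +1.7 to +4.8 and all-gaps −1.8 to −5.5. With 2/3 implants in 70/30%, any-gap is 1.04–1.12 and all-gaps 0.87–0.96.

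**5. What removes it.** Within one implant count, step 3 has the same any-implant prevalence in both groups, so adjusting for count removes the bias. Counting disease only at one pair gives 1 − 0.9² = 19% in every patient, which also removes it. In the three settings of step 4, the count-stratified Mantel-Haenszel odds ratio is 0.99–1.02, and so is the index-pair odds ratio.

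**6. With a true effect.** Raise disease odds at implants beside a narrow gap so that a two-implant pair has odds ratio 2.49, with spacing unrelated to count. The unadjusted patient-level odds ratio is 2.4–2.9 (any gap), 1.4–1.8 (all gaps) or 1.8–2.1 (random gap, any-implant disease). Power at 90 per group is 79–90%, 18–48% and 48–66%. The any-gap power is partly count bias: with no effect, that rule puts 8–22% of diseased narrow-group patients there with no diseased implant beside a narrow gap.

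**The case against.** Four points on the other side have force.

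- **One pair, one gap.** A patient with a single contiguous pair is classified without ambiguity. A reader might infer that every patient with two or more implants is affected. That is not so: the classification problem needs at least two gaps, and the documents do not give the share of such patients. For a one-pair patient, only the second question can remain: whether disease at another implant elsewhere counts.
- **The rule may exist.** Section numbers run from 4.7 to 4.11. Section 4.7 mentions study variables that are listed nowhere, and section 4.11 plans tests for continuous and ordinal variables that no available section defines. Sections 4.8 to 4.10, if they exist, are where an index-pair rule would sit. A proven omission from the full protocol cannot be claimed.
- **The outcome level is not fixed.** A reader might infer that the plan chose a patient-level outcome at odds with its aim. The term appears only in section 4.5, describing earlier studies. Section 4.11 names no unit, and the aim points to the contiguous implants. The supported criticism is that unit and outcome are unspecified.
- **The signs are not general.** A reader might infer that an any-gap rule always inflates, an all-gaps rule always deflates and a random gap is safe. Those signs hold only if spacing is unrelated to implant count. The second and third rows of each table in the working break them, and the documents say nothing on that relation.

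It is also fair that every magnitude rests on assumed inputs and that some are small. None of this supplies the missing rule.

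**Conclusion.** The point stands in limited form. For patients with more than one gap, the available text does not say which gap classifies the patient, does not confine disease to the implants beside it, and does not name implant count as a covariate. An unadjusted patient-level comparison can then be biased with no distance effect.

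Direction and size cannot be taken from the documents. On the assumed 2/3/4 mix, null odds ratios ran from 0.69 to 1.45 across rules and spacing patterns. None of these illustrations reaches the planned 20-point difference, so the text does not support saying that count alone would produce the hypothesised result; but assumed inputs do not set an upper bound either. The problem is nil if each patient contributes exactly one pair with disease counted only there, or if an unseen section says so. It should be fixed before data collection; confidence is medium.

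**What to change.** **Preferred.** In sections 4.4 and 4.11, make the contiguous pair the unit. Exposure is that pair's distance, with implant type for the specific objective. The outcome is disease at its two bordering implants. Fit a logistic GEE or mixed model clustered on patient, with number of implants as a covariate.

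**Minimum, if the patient stays the unit.** State which gap classifies a patient with several, count disease only at the two implants beside it, and include number of implants in the logistic model.

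**Alternative.** Choose one index pair per patient by a prespecified random rule and count disease only there. This keeps one row per patient and the planned tests, but discards data.

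**Cost.** Full-mouth probing already reaches each implant. Distance must be recorded for every pair used, while radiographs are planned only where needed. GEE would replace the chi-square as the main test.

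The 24% vs 44% basis must be restated for the chosen unit. In the assumed mix, 24% any-implant prevalence is about 19–20% for an index pair. At odds ratio 2.49 the formula in step 1 gives 100 per group for 18.6% vs 36.2%, and 95 for 20.3% vs 38.8%; 90 per group then has 76–78% power. If a neighbouring narrow gap also affects the shared middle implant, the index-pair odds ratio falls to 2.1–2.3 and power at 90 per group to 61–71%.

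In simulated studies of 180 patients with group sizes as they fell and spacing unrelated to count, power was 77–82% for the pair-level GEE and 58–68% for the index pair, with type I error of 3.9–5.7%. That is the case for the pair-level analysis, on assumed inputs.

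### Inter-implant distance is analysed only as ≤ 3 mm versus > 3 mm, so the plan cannot show how prevalence varies with distance or whether another cut fits better

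*Combined protocol and SAP*

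**What the plan says.** The end of the Introduction gives the aim as to "analyze contiguous dental implants and its peri-implant status depending on different inter-implant distances". The Background adds that "understanding a minimal threshold for inter-implant distance depending on type of implant might be critical to prevent such diseases". The formal objectives are narrower. Section 2.1 asks for an association between distance and prevalence, section 2.2 brings in implant type, and the hypotheses in sections 3.1 and 3.2 fix the cut in advance at 3 mm.

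Section 4.4 then reduces distance to two levels. Patients "will be classified based on the inter-implant distance": "Group 1: Inter-implant distance ≤ 3 mm" and "Group 2: Inter-implant distance > 3 mm". Section 4.5 sizes the study as a comparison of two proportions, 44% against 24%, with 90 patients per group.

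Section 4.11 follows the same coding: "Comparisons between study groups will be performed using Chi-square test" for categorical variables and, for the final logistic model, "The study group and other potential cofactors will be included as independent variables". It names no analysis of distance in mm, in several categories, as a spline or at another cut. Its general lines on continuous and ordinal variables do not mention distance.

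The Introduction gives the source of the spacing advice: "to prevent esthetic complications, it is advised to leave 3–4 mm of space between dental implants".

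**The concern.** With one binary split, 0.8 mm and 2.9 mm count as the same exposure, and 3.1 mm and 8 mm as the same comparator. Two consequences follow.

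- **A significant difference is ambiguous.** A steady decline in risk with distance, a step at 2 mm and a step at 3 mm can all produce a difference between the groups. The result could be read as confirming 3 mm as the threshold when the analysis has not compared 3 mm with any alternative.
- **A null result is ambiguous too.** If risk rises only well below 3 mm, Group 1 mixes affected and unaffected patients. The contrast shrinks, and a real relation could be reported as no association.

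The Introduction ties the 3–4 mm advice to esthetics, and the authors state that to their knowledge no study has related inter-implant distance to peri-implant disease. The shape of the relation is therefore open, and the planned analysis does not describe it.

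**Working it through.** **Inputs.** From section 4.5: prevalence 24% and 44%, two-sided alpha 5%, power 80%, 90 per group (180 in total), loss 12%. From section 4.4: the cut at 3 mm. The documents give no distribution of distance. The assumption here is a normal distribution with SD 1 mm centred on 3 mm, which gives the planned 90/90 split; the variations are stated.

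**1. The plan's own figure.** The usual two-proportion formula (two-sided, no continuity correction) gives 87 per group, 174 in total, slightly below the stated 90 and 180. Power at n = 90 per group is

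Φ{[d√n − 1.96√(2p̄(1−p̄))] / √(p₁(1−p₁) + p₂(1−p₂))}.

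With d = 0.20 and p̄ = 0.34 this is Φ{(1.897 − 1.313)/0.655} = Φ(0.892) = 81.4%. The two-group test is adequately sized if the group prevalences are as planned.

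**2. Smooth relation.** Take risk as linear in distance on the logit scale and solve for 44% below and 24% above the cut. The slope is −0.589 per SD. Simulated power with 180 patients is about 82% for the two groups and 95% for linear distance. With 158 patients (180 × 0.88) it is about 76% and 91%. If 30% or 70% of patients lie at or below 3 mm, it is about 74% against 91%, or 73% against 94%, with 180 patients.

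For a normal exposure split so that a share q lies below the cut c (on the standard normal scale), the relative efficiency of the split is φ(c)²/[q(1−q)]:

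- q = 0.5: 0.399²/0.25 = 0.64, so 180 × 0.64 ≈ 115 patients' worth of information
- q = 0.3 or 0.7: 0.348²/0.21 = 0.58, so 180 × 0.58 ≈ 104

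**3. Step away from 3 mm.** Let prevalence be 44% at or below a step t and 24% above it. Group 1 prevalence is then 0.24 + 0.20 × Φ(t − 3)/0.5.

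- t = 2.0 mm: 0.24 + 0.20 × 0.1587/0.5 = 30.3%, against 24%. Power is Φ{(0.602 − 1.233)/0.628} = 16%.
- t = 2.5 mm: 0.24 + 0.20 × 0.3085/0.5 = 36.3%, against 24%. Power is 44%.
- With SD 2 mm instead of 1 mm, power is 44% for t = 2.0 and 64% for t = 2.5.

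**4. Whether modelling distance does better.** Simulated power with 180 patients and SD 1 mm (two-group power from the formula or simulation; overall test for the 3-knot spline):

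| True step | Two groups | Linear distance | Spline |
|---|---|---|---|
| 2.0 mm | 15–16% | 32% | 36–38% |
| 2.5 mm | 42–44% | 53% | 50% |
| 3.0 mm | 80–81% | 60–61% | 52–53% |

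Modelling distance gains when the step lies below 3 mm, though power stays low. It loses clearly when the step is exactly at 3 mm. In these step scenarios the spline's nonlinear term reached significance in only about 8% to 21% of simulated studies, so 180 patients would seldom separate a step from a gradual trend.

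**The case against.** The strongest reply is that the design is coherent as written. The objective is an association, the hypothesis presets 3 mm, and the groups, sample size and model follow from it, apart from the hypotheses using < 3 mm where the groups use ≤ 3 mm. Testing whether a clinical spacing convention also bears on disease is a fair question. If the truth is a step at 3 mm, the two-group test is the better one. All of this stands, and it is why the 3 mm contrast should remain primary.

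Three stronger readings are tempting, and the documents do not support them.

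- **That the study fails an objective to find a threshold.** The threshold appears as motivation in the Background and in neither objective. The gap is between rationale and analysis.
- **That the Introduction shows 3 mm to be the wrong cut.** The cited work at 1, 2 and 3 mm concerns bone level around platform-switched implants, whereas the Introduction says platform-matched implants were used in this study.
- **That distance is recorded too coarsely, or that measurement error makes the split unsound.** The available text goes from section 4.7 to 4.11, so the precision of the measurement cannot be judged. Error in measuring distance would also weaken a model in mm.

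The reply does not remove the remaining point: even a plain association objective is only coarsely served by two groups.

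**Conclusion.** The point holds as a worthwhile improvement to the analysis and does not invalidate the primary comparison. That distance enters only as two levels is plain from sections 4.4 and 4.11. As a result, the study can say whether prevalence differs across 3 mm, but not how prevalence varies with distance or whether another cut fits better.

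The size depends on the true shape, which is unknown. The two groups cost about 13 percentage points of power under a smooth relation (82% against 95%) and about half of an already low power with a step at 2.0 mm (16% against 32–38%). They gain about 20 points or more if the step is exactly at 3 mm (80% against 60% and 53%). These figures rest on the assumed normal distribution. The two-group coding itself does not depend on that assumption. A reader might infer that a distance model would locate the threshold; at 180 patients, and still more within each implant type, it can do so only roughly.

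**What to change.** - Keep ≤ 3 mm versus > 3 mm as the primary contrast.
- Add to section 4.11 a prespecified secondary logistic model with distance in mm: linear, and a restricted cubic spline with 3 knots at prespecified positions. Present the fitted prevalence-versus-distance curve with its 95% confidence interval.
- Label any curves by implant type exploratory.
- State that a significant 3 mm contrast alone will not be presented as evidence that 3 mm is the threshold.

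The cost is a few lines in section 4.11 and one extra model with one or two more terms. If distance is kept in mm when groups are assigned, no new data are needed; the available text does not show whether it is. The main limitation is that any threshold will be located with little precision.
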